## 4.3 Endpoints

i. Predictor variables:

- a. Biopsy approach
  - i. *Variable type:* Dichotomous (categorical)
  - ii. *Potential outcomes:* Transperineal vs Transrectal
- b. Location of target lesion within the prostate is a prominent consideration for targeting accuracy, as lesions in the anterior prostate are known to be difficult to access using a posterior approach (transrectal biopsy).
  - i. *Variable type:* Categorical
  - ii. *Potential outcomes:* (Left vs right) + (Anterior vs posterior) + (apex vs midgland vs base)

ii. Outcome variables:

- a. Length of core-cancer involvement - A larger amount of cancer within each core as a result of improved lesion targeting provides better disease characterization. Data regarding core cancer length measurements in transperineal targeted biopsy is limited. Previous studies have shown median CCL in MRI-targeted transperineal biopsy to be 2mm (range 1-5mm). However, MRI-guided biopsies were performed under cognitive US-MRI fusion and thus did not benefit from automated image coregistration, which was shown to significantly increase mean CCL. To our knowledge there is no precedent for estimation of CCL in targeted transperineal biopsies using automated US/MRI fusion.
  - i. *Variable type:* Continuous
  - ii. *Scale:* millimeters
  - iii. *Validity:* Greater tumor length per core provides better diagnostic information and has been shown to correlate with Gleason score and pathologic stage at radical prostatectomy.
  - iv. *Source:* Histological analysis (pathologist's report)
- b. Number of cancers detected using each approach- The relative cancer detection rates (CDRs) between approaches correlate to the sensitivity of detecting cancer in high risk foci, and should be directly compared between the two modalities as a marker of targeting accuracy.
  - i. *Variable type:* Continuous
  - ii. *Potential outcomes:* 0-100%
  - iii. *Validity:* Since each lesion serves as its own control, a higher percentage of cancer-positive results using a given approach directly corresponds to accuracy of targeting using that technique
  - iv. *Source:* Histological analysis (pathologist's report)
- c. Concordance of Gleason score between biopsy and prostatectomy- This measurement correlates to the accuracy of the biopsy technique compared to pathological analysis of the excised prostate gland (gold standard) and is the ultimate metric for **characterization of disease**. However, this is likely to include only a small number of study subjects and therefore may not demonstrate a definitive difference between the two techniques.
  - i. *Variable type:* Categorical

- ii. *Potential outcomes:* True concordance, upstage at final pathology, downstage at final pathology
- iii. *Source:* Histological analysis (pathologist's report)

#### **4.4 Follow-up**

The first clinical follow-up visit will be scheduled 1 week after biopsy. At that time the patient's clinical condition will be assessed according to standard of care post-biopsy evaluation. All study participants will be evaluated for additional complications to ensure that the targeted biopsies do not confer additional risk for complications. However, given that the maximum number of biopsies will be within the standard of care range, we do not anticipate an increase in complication rates. Biopsy results will be revealed to the patient at that time.

The primary endpoint of the trial will be assessed upon accrual and biopsy of the planned number of study participants. The primary objective will be assessed by quantifying the core cancer lengths of positive biopsy results (diagnosis of CaP, Gleason 3 or higher, in any given core) for each technique of targeted biopsy. Secondary endpoints will be evaluated via rate of positive biopsy using transperineal versus transrectal targeted techniques for prostate sampling. Furthermore, cancer characteristics including Gleason score and disease volume will be evaluated across techniques. All adverse event data will also be recorded.

Patients diagnosed with CaP will be offered standard of care treatment options as based upon the stage and grade characteristics of the identified disease. Targeted biopsy results that reveal CaP will be considered in the same fashion as CaP diagnosed with standard of care biopsy. All recommendations regarding the appropriate management of any CaP diagnosed will then be based upon biopsy features and patient decision.

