#### Additional Observations:

1. Occurrence of adverse events.
2. Time spent in performing each biopsy technique.
3. Correspondence of MRI suspicion score to presence of clinically significant cancer detected on biopsy

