The targeted biopsies will require 4 cores per lesion for each patient. A maximum of three mpMRI lesions will be allowed to be targeted. It is very rare (<5% of positive mpMRI) for there to be more than three lesions identified on mpMRI. The 4 cores taken per targeted lesion is the current standard at the Smilow Prostate Cancer Center. Typically, a biopsy will be done through one approach (transrectal or transperineal). For the purposes of this study, both approaches will be used per targeted lesion. However, only two cores will be taken for each approach which will not result in any extra cores taken for research purposes. As both approaches are considered routine, performance of both approaches during a biopsy sitting should not result in an increased likelihood of comorbidity and will not extend a subject's time under anesthesia by any significance.

Risks of performing the two targeted biopsy approaches in one setting are the same risks inherent to traditional systematic standard care prostate biopsy, including bleeding, infection, urinary retention, and voiding dysfunction.

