## **6.2 Study Timeline**

- i. Visit 1 (week 0)
  - a. Baseline visit to determine patient eligibility based on careful review of patient medical history and risk for prostate cancer. If available, patient mpMRI will be reviewed as well. This visit will occur as part of their standard clinical care with the investigator for suspected or known prostate cancer. The research team will review the consent form with the potential subject and answer all questions. Once eligibility is confirmed and the patient agrees to participate in the study, informed consent is signed, and the patient will be scheduled for prostate biopsy at their next visit (2-4 weeks).
  - b. If no mpMRI is available, the patient will be scheduled for this imaging study as per our institution's standard of care before finally determining eligibility. This will be done regardless of participation in the study.
- ii. Visit 2 (week 2-4)
  - a. Approximately 2-4 weeks after the initial visit, each subject will return for prostate biopsy. All biopsies will be done in one operative session and will be performed as outpatient procedures.
- iii. Visit 3 (week 4-5)
  - a. All study participants will have a follow up visit approximately one week following biopsy for clinical evaluation of recovery from biopsy and to review biopsy results. At this point, all patients will be managed according to standard of care based upon biopsy results.

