## **6.3 Evaluation During and After Intervention**

Subjects will be monitored by a qualified anesthesiologist during and after the procedure. Following the biopsy, patients will be relocated to the recovery bay adjacent to the procedure room for observation. All patients will be evaluated clinically one week after

biopsy to assess for biopsy complications including risk of infection, persistent hematuria or rectal bleeding. Any identified complications will be recorded and treated according to severity.

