### **7.3 Potential Adverse Events**

This is a minimal risk study where loss of confidentiality is a potential risk. The PI will adhere to a data monitoring plan to ensure there is no breach in confidentiality.

-There is also risk associated with prostate biopsy (transrectal or transperineal). This includes bleeding, infection, urinary retention, and erectile dysfunction. Because it is not standard to have both approaches done in one sitting for a biopsy, the PI will also monitor the study for an unexpected increase in risk for these potential adverse events.

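### With one scheduled check after discharge, both routes in every man and no reference rate, the trial can describe complications of the combined session but cannot establish that it adds no risk

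*Combined protocol and SAP*

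**What the plan says.** The plan makes three statements about the safety of the session.

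- Section 4.4 (Follow-up): "All study participants will be evaluated for additional complications to ensure that the targeted biopsies do not confer additional risk for complications". It expects no rise in complications because the number of cores stays within the usual range.
- Section 4.2 (Intervention): "As both approaches are considered routine, performance of both approaches during a biopsy sitting should not result in an increased likelihood of comorbidity".
- Section 7.3 (Potential Adverse Events) concedes that using both routes in one sitting is not standard. It lists the risks of biopsy, "This includes bleeding, infection, urinary retention, and erectile dysfunction", and undertakes that "the PI will also monitor the study for an unexpected increase in risk for these potential adverse events".

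On timing, section 4.4 states: "The first clinical follow-up visit will be scheduled 1 week after biopsy". Section 6.3 describes the content of that visit as an evaluation after "biopsy to assess for biopsy complications including risk of infection, persistent hematuria or rectal bleeding". Section 6.2 (Study Timeline) lists no study visit after this one.

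On rank, "Occurrence of adverse events" stands under Additional Observations in section 2.1. It is neither a primary nor a secondary objective.

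**The concern.** Words such as additional risk and unexpected increase are comparative. They need something to compare with, and they need events to be collected over a defined period. The plan provides no comparator and only a short scheduled period.

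The reason given in section 4.4 also misses the new feature of the session. The core count is unchanged, but using two routes in one sitting is what section 7.3 calls non-standard.

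What is at stake is how the safety table will be read. Lower infection risk is part of the stated case for the transperineal route (Secondary Objectives; section 3.1). A short list of events could be taken as evidence that the transperineal route, or the combined session, is safe. The data would support only a rate for the combined session, observed systematically for about a week.

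**Working it through.** **1. Is there a comparator?** Sections 4.1 and 4.2 give every man both routes in one session. No group has one route only. Section 4.5 (Biostatistics) contains no safety analysis, reference complication rate or margin. Section 8 has no formal stopping rule and does not define what would count as more than minimal risk at its review after 5 patients.

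**2. What is collected, and when?**

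| Time | What the plan provides | Section |
|---|---|---|
| Before biopsy | PSA history, rectal examination, MRI, medical history; no erectile function measure | 6.1, 6.2 |
| Procedure to discharge | Anesthesia monitoring, recovery observation, voiding trial | 4.2, 6.3 |
| About 1 week | Clinical visit; repeat voiding trial if the first failed | 4.2, 4.4, 6.3 |
| After that | No scheduled contact; log of adverse events, follow-up of serious events, quarterly review | 7.2, 8 |

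Erectile dysfunction is named in section 7.3 but not among the examples in section 6.3. Without a baseline, a change cannot be measured at any time.

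**3. Is the visit timing consistent?** Biopsy at week 2 to 4, plus one week, gives week 3 to 5. Section 6.2 labels Visit 3 as week 4 to 5. The label omits week 3, which is when a man biopsied at week 2 would be due.

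**4. The plan's own sample size.** Inputs from section 4.5: mean difference 1.0 mm, SD 2.4 mm, alpha 5% (two-tailed test), power 80%.

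n = ((1.960 + 0.842) × 2.4 / 1.0)² = 45.2, rounded up to 46 cancer-positive lesions.

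This reproduces the stated 46. It concerns core cancer length only; there is no counterpart for complications.

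**5. What zero events would show.** The exact upper limit with 0 events in n men is 1 − a^(1/n), with a = 0.05 (one-sided 95%) or 0.025 (two-sided 95%).

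| Men biopsied | One-sided | Two-sided |
|---|---|---|
| 80 (planned recruitment, section 4.5) | 1 − 0.05^(1/80) = 3.7% | 1 − 0.025^(1/80) = 4.5% |
| 60 (assumed) | 4.9% | 6.0% |

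The 80 allows for screen failures, so fewer men may be biopsied.

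**6. What a reference rate would add.** The documents give none, so the rates below are assumptions. The power column is for an exact one-sided 0.025 test in 80 men against a fixed rate p0 when the true rate is 2 × p0. The last column is 1 − (1 − p)^5 with true rate p = p0.

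| Assumed p0 | Reject at this many events or more | Power for a doubling | Chance that the first 5 men show any event |
|---|---|---|---|
| 1% | 4 | 8% | 5% |
| 2% | 5 | 22% | 10% |
| 5% | 9 | 41% | 23% |
| 10% | 15 | 65% | 41% |

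Even with a fixed benchmark and complete capture, a doubling would often go undetected.

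**The case against.** The strongest reply is that safety is not an objective here. Adverse events are an additional observation, the section 4.4 sentence describes patient monitoring, and the plan claims no safety hypothesis, margin or test. The paired design is deliberate, because each lesion acts as its own control for the primary comparison. This stands. It limits the point to what the plan says and reports about safety, and leaves the primary analysis untouched.

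Several stronger readings are tempting, and the documents do not support them.

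- *Complications are checked only at one week.* Sections 4.2 and 6.3 add checks up to discharge, and section 4.4 calls the one-week visit the first. What is missing is a scheduled later contact.
- *Later events are lost altogether.* Section 7.2 keeps a log throughout the study and follows serious events to their outcome. The men are also under the investigators' care (section 6.1). Capture is possible but unplanned.
- *No event can be assigned to a route.* Section 3.1 links rectal bleeding to the transrectal route, and section 6.3 looks for it. Section 7.1 grades relation to the procedure, though not by route. The difficulty is with systemic events such as infection, and with retention.
- *Retention is not properly measured.* The voiding trial before discharge, repeated at about one week after a failure, measures it directly.
- *The Visit 3 label shows that men are followed for unequal times.* The text under that label still says about one week after biopsy. The label is a minor inconsistency.
- *The zero-event limits measure the follow-up gap.* They do not. They would apply to any cohort of that size, however long it was followed.

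A longer window alone would not supply a comparator. That is why the wording of the claim must change as well as the follow-up.

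**Conclusion.** The point holds in limited form. The trial can report complication rates for a two-route session. It cannot establish that the session adds no risk, cannot recognise an increase when no baseline rate is named, and cannot attribute infection or retention to one route. The lack of a comparator is the main weakness; the single scheduled check after discharge and the missing erectile baseline are secondary.

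On precision, zero events would leave rates up to 3.7% (80 men) or 4.9% (60 men, assumed) compatible with the data at one-sided 95%. Both figures presume complete capture. The number of events after the one-week visit cannot be estimated from the documents. The power and first-5 figures depend on the assumed rates of 1% to 10%.

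This is a worthwhile and inexpensive improvement to safety capture and reporting. It does not threaten the primary result.

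**What to change.** 1. **Add one later look.** Existing staff make a chart check or telephone call 30 days after the biopsy date, covering infection, emergency visit or admission, catheter status and bleeding. The documents fix no window, so 30 days is a proposal for the study team to agree. Record erectile function at baseline and at this contact, or remove it from the monitored list in section 7.3.

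2. **Replace the assurance in section 4.4.** Suggested text: *Complication rates describe the combined two-approach session and are not attributed to either approach. They are reported with exact 95% confidence intervals, using men actually biopsied as the denominator.* If the institution already holds a single-approach rate, cite it as context only. Collecting such a rate in the same way would need a second cohort and is not part of this proposal.

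3. **Minor:** reconcile the Visit 3 label in section 6.2 with one week after a biopsy at week 2 to 4.

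The cost is one call or chart check per man and some redrafting. More events will be recorded, and the safety statement will be weaker than the present one.

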#### **4.5 Biostatistics**

##### **Sample size justification**

Evaluation of cancer-core length will be the primary endpoint, as reported above. The necessary sample size will be powered to observe a significant difference in CCL between techniques. The limited available data regarding CCL obtained from transperineal targeted biopsy may not serve as an accurate estimate within our population due to potential differences in targeting techniques as well as patient demographics and selection criteria for biopsy.

Our data from a recent study of patients receiving both targeted and systematic transrectal biopsies demonstrated that the mean CCL per positive core per patient is  $4.7 \pm 3.3$ mm in MRI-targeted transrectal biopsies compared to  $2.8 \pm 2.4$ mm in systematic biopsies. The mean difference of 1.9mm was significant ( $p = 0.03$ ) in a cohort of 67 biopsy-naïve men out of 125 recruited at our institution over 9 months, and likely reflected improved sampling of cancer foci. Similarly, retrospective analysis of 601 MRI-targeted transrectal biopsies at our institution demonstrates that the mean difference between the largest CCL

and second largest CCL found on targeted biopsy of the same lesion is  $2.1 \pm 2.4\text{mm}$ . This difference in CCL may also be considered as reflective of a discrepancy in lesion targeting accuracy between two cores. The average of these two estimates of difference in CCL (1.9mm and 2.1mm) is 2.0mm.

For the present study, a conservative estimate of the mean difference in CCL obtained by transperineal vs transrectal targeted biopsy is 1.0mm, or half of the aforementioned difference of 2.0mm. Assuming a tolerance for  $\alpha$  error of 5%, 80% power, and a mean difference of  $1.0 \pm 2.4\text{mm}$ , a sample size of 46 cancer-positive lesions would be needed to demonstrate a difference in targeting ability between the two biopsy techniques.

Positive results will be compared on a per-lesion basis, where the largest CCL of the two cores taken from each approach will be compared. Preliminary data from MRI-targeted biopsy since 2012 at the NYU SPCC has demonstrated approximately 55% and 95% cancer detection rate among patients with MRI suspicion scores of 4 and 5, respectively. Additionally, the average number of cancer-positive lesions among men with prostate cancer detected on targeted biopsy is 1.2. Given the approximate time-course for the study, accrual rate, cancer detection rate in our previous trial, and potential screen failures, we anticipate that recruitment of 80 patients will be feasible and provide sufficient power to demonstrate a difference of 1.0 mm in cancer-core length between the two techniques. This sample size also accounts for potential screen failure for patients consented who have not yet had their standard of care MRI of the prostate.

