### **Statistical analysis for primary objective**

Measurements of cancer-core length from transrectal and transperineal biopsies may be compared using a two-tailed, paired samples T test or Wilcoxon Signed Rank Test in order to accept or reject the hypothesis that transperineal biopsy provides higher CCL per positive core than transrectal biopsy.

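### Section 4.5 sizes the trial with an SD of 2.4 mm that is not shown to be the SD of the difference tested, so the 80% power at 46 lesions is unsupported

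*Combined protocol and SAP*

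**What the plan says.** The sample size justification in Section 4.5 gives two estimates of a CCL difference. One is 1.9 mm, between MRI-targeted (4.7 ± 3.3 mm) and systematic (2.8 ± 2.4 mm) transrectal biopsy. The other comes from 601 targeted transrectal biopsies, where the mean difference between the largest CCL "and second largest CCL found on targeted biopsy of the same lesion is" 2.1 ± 2.4 mm. The plan averages these to 2.0 mm, halves the result to 1.0 mm, attaches ± 2.4 mm without saying where it comes from, and states that "a sample size of 46 cancer-positive lesions would be needed to demonstrate a difference in targeting ability between the two biopsy techniques".

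The comparison is per lesion, "where the largest CCL of the two cores taken from each approach will be compared". The test is a "two-tailed, paired samples T test or Wilcoxon Signed Rank Test", used to judge whether "transperineal biopsy provides higher CCL per positive core than transrectal biopsy".

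On recruitment, the plan cites "approximately 55% and 95% cancer detection rate among patients with MRI suspicion scores of 4 and 5, respectively" and says that "the average number of cancer-positive lesions among men with prostate cancer detected on targeted biopsy is 1.2". It concludes that "recruitment of 80 patients will be feasible and provide sufficient power to demonstrate a difference of 1.0 mm in cancer-core length".

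**The concern.** A paired test needs the SD of the paired difference. The value 2.4 mm appears twice earlier in the justification, and neither use is that SD:

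- The SD of systematic-biopsy CCL describes a level, not a difference.
- The SD of the largest-minus-second-largest gap describes a difference whose sign has been removed by ordering the cores. Its spread is measured around 2.1 mm. A signed difference between exchangeable cores is centred on zero, so the 2.1 mm mean of the gap becomes part of the spread.

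The documents give neither the SD of the signed best-of-two difference nor a within-lesion correlation from which to derive it. Both the 46 lesions and the adequacy of 80 patients depend on this number. As written, a reader cannot tell what difference the trial could detect, and a null result would be hard to interpret.

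**Working it through.** **Inputs.** From the sample size justification: alpha 5%, power 80%, difference 1.0 mm, SD 2.4 mm, gap 2.1 ± 2.4 mm, 80 patients, 1.2 positive lesions per man with cancer, detection 55% (score 4) and 95% (score 5). The test is two-sided, from the primary analysis section.

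**1. The plan's own figure.** n = (1.960 + 0.842)² × SD²/δ² = 7.849 × 2.4²/1.0² = 45.2, so 46. By the noncentral t, power at 46 is 0.79 and 80% needs 48. The figure reproduces, but with no slack: 80% t power at 46 requires an SD of at most 2.37 mm.

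**2. What the gap figures imply in one illustrative case.** Assume that:

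- the 601 biopsies had four exchangeable cores per lesion;
- the gap includes lesions with one positive core (second core 0 mm);
- lesions positive by either approach count, with a miss scored 0 mm;
- transperineal biopsy adds a constant shift.

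Let G be the gap and D the signed best-of-two difference after splitting the four cores 2 versus 2. The largest core falls in one arm, and the other arm's best is at most the second largest overall, so |D| ≥ G. Hence E[D²] ≥ E[G²] = 2.1² + 2.4² = 4.41 + 5.76 = 10.17. In an all-transrectal history D has mean zero, so SD(D) ≥ √10.17 = 3.19 mm. A constant shift leaves the SD unchanged.

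**3. Consequence for the paired t test (1.0 mm, two-sided 5%, noncentral t).**

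| SD (mm) | Power at 46 | Lesions for 80% | Detectable at 46, 80% power (mm) |
|---|---|---|---|
| 1.8 | 0.96 | 28 | 0.76 |
| 2.4 | 0.79 | 48 | 1.01 |
| 2.63 | 0.71 | 57 | 1.11 |
| 3.19 | 0.55 | 82 | 1.35 |
| 3.57 | 0.46 | 102 | 1.51 |
| 4.0 | 0.38 | 128 | 1.69 |

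The 0.55 is a normal-theory value. Simulating randomly signed gamma gaps of 2.1 ± 2.4 mm with a 1.0 mm shift gives about 0.57 for the t test and 0.77 for Wilcoxon at 46 lesions.

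**4. Other readings.**

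- *Two-core history.* The 3.19 mm is then the one-core-versus-one-core signed SD. Best-of-two gives 3.19 × √(1 − 1/π) = 2.63 mm for normal cores, and (3.19/√2) × √2.5 = 3.57 mm for exponential cores.
- *Simulated histories* fitted to the gap and to positive-core CCL 4.7 ± 3.3 mm, with randomly missed cores and a constant 1.0 mm shift:
  - Four cores, positive by either approach: SD 3.95–4.01 mm; power at 46 is 0.40–0.42 (t) and 0.52–0.55 (Wilcoxon).
  - Four cores, positive by both: SD 1.73–2.67 mm; t power 0.71–0.96 with 46 analysable lesions, but only 62–71% of positive lesions qualify.
  - Two cores, positive by either: SD 1.85–2.63 mm; power at 46 is 0.73–0.93 (t) and 0.81–0.99 (Wilcoxon).

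These fits are illustrative. They combine figures from two cohorts, and the four-core fits need 41–49% missed cores, which no document supports.

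**5. What 80 patients might yield.** 80 × 1.2 × detection, with no screen failure, gives 53 lesions at 55%, 72 at 75% (an assumed midpoint) and 91 at 95%. The largest SD compatible with 80% t power is 2.55, 2.99 and 3.37 mm respectively. Reaching 82 lesions needs 82/96 = 85% detection, or 82/86.4 = 95% with an assumed 10% screen failure. Counting only lesions positive by both approaches, 53 positive lesions leave 33–38 (53 × 0.62 to 53 × 0.71).

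**The case against.** The likely origin of the 2.4 mm is not obscure. The justification presents the 2.1 ± 2.4 mm gap as reflecting a targeting discrepancy between two cores, then carries on with 1.0 ± 2.4 mm. That is probably right, but it explains the number without making it the SD of the tested difference.

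The stronger objection is to any firm claim of low power, and most of it stands:

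- Sections 3.2 and 4.2 describe four cores per lesion as site practice, but nothing says the 601 biopsies had four, or how lesions with one positive core entered the gap.
- The wording about positive results and positive cores in Sections 4.4 and 4.5 may point to lesions positive by both approaches, for which the SD could be below 2.4 mm.
- Wilcoxon is a named alternative and does better with skewed differences: about 0.77 at 46 and 0.82 at 53 in the signed-gamma case.
- If transperineal biopsy wins more often rather than adding a constant, the SD falls to √(10.17 − 1.0²) = 3.03 mm, and t power at 46 is about 0.59, or 0.61–0.66 with skewed gaps.

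A reader might infer that power is at most 0.55. The documents do not support that as a ceiling, because it depends on the conditions above and on normal theory. Nor do they support 3.2 mm as the correct replacement.

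**Conclusion.** The point holds as one about an unsupported input. The formula is correct. The 2.4 mm is not shown to be the SD of the signed best-of-two difference, and the only SD of a difference on offer belongs to another quantity, so the 80% power at 46 lesions has no stated basis.

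The size of the error cannot be fixed from the documents. Under the four assumptions in step 2 the SD is at least 3.19 mm; at that value t power is about 0.55–0.57, about 82 lesions are needed, and the detectable difference at 46 is about 1.35 mm. Wilcoxon power ranges from about 0.77 (signed gamma gaps) down to 0.52–0.55 (fitted four-core models). With a two-core history, or an analysis limited to lesions positive by both approaches, the shortfall may be absent, though the latter leaves fewer lesions.

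A reader might also conclude that 80 patients are too few. That does not follow: all three illustrative yields of positive lesions in step 5 exceed 46, and the plan gives no detection rate for score 3 lesions, which are eligible, and no screen-failure rate. The claim is unsupported, not shown false. It should be fixed; confidence is medium.

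**What to change.** In Section 4.5:

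- State the source of the 2.4 mm and the number of cores per lesion in the 601 biopsies.
- Define the analysable lesions: positive by either approach with a miss counted as 0 mm, or positive by both.
- Replace 2.4 mm with the SD of the signed best-of-two difference, recomputed from those biopsies on that lesion set, using a random 2-versus-2 split where four cores exist.
- Name the primary test. For it, restate power for 1.0 mm and the detectable difference at 46 lesions and across the counts that 80 patients can yield, giving the assumed detection rates (including score 3) and screen-failure rate.
- If the data cannot be re-run, show power over SDs on both sides of 2.4 mm, for example 1.8–4.0 mm including 3.2 mm, labelled as an assumption.

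The cost is rewording and a short analysis of data the site already holds. No extra patients are required. The stated power may become less favourable.

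### The per-lesion CCL test and the 46-lesion calculation treat several lesions in one man as independent; if the paired difference varies randomly between men, type I error modestly exceeds 5%, and a patient-clustered standard error corrects this cheaply.

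*Combined protocol and SAP*

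**What the plan says.** Section 4.5, Sample size justification, fixes the unit of the primary analysis: "Positive results will be compared on a per-lesion basis". For each lesion, the longer CCL from one approach's two cores is set against the longer CCL from the other's. Under the primary objective in 4.5, the measurements "may be compared using a two-tailed, paired samples T test or Wilcoxon Signed Rank Test". The sample size uses a mean paired difference of 1.0 mm, SD 2.4 mm, 5% alpha and 80% power, and concludes that "a sample size of 46 cancer-positive lesions would be needed".

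The same section reports that "the average number of cancer-positive lesions among men with prostate cancer detected on targeted biopsy is 1.2", and section 4.2 caps targeting at three lesions per man, so the plan expects some men to supply more than one pair. On enrolment it holds that "recruitment of 80 patients will be feasible and provide sufficient power to demonstrate a difference of 1.0 mm". No section gives a design effect, a clustered standard error, a mixed model or a rule of one lesion per man.

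**The concern.** Pairing deals with two approaches applied to one lesion. It does nothing about several lesions in one man. The quantity that matters is the ICC of the paired differences, because anything that shifts both approaches equally has already been subtracted out.

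That ICC would be positive if the size of the transperineal-minus-transrectal difference varied at random between men. Examples are patient-specific variation in registration, or in how far the prostate shifts after the repositioning described in section 4.2. The unclustered standard error would then be too small, the confidence interval too narrow and the type I error above 5%. Recruiting more men would not remove this.

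**Working it through.** **1. The plan's own figure.** Inputs from section 4.5: difference 1.0 mm, SD 2.4 mm, two-sided 5%, power 80%. n = (1.96 + 0.8416)² × (2.4/1.0)² = 45.2, rounded up to 46. The figure reproduces, as a calculation for independent pairs. Exact paired t power at 46 is 79.0%.

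**2. Lesion mixes (assumed).** 46/1.2 is about 38 men. The documents do not give the distribution of positive lesions per man, so three mixes of 46 lesions in 38 men are used, written as men with 1/2/3 lesions: 30/8/0, 31/6/1 and, as an extreme, 34/0/4.

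**3. Type I error of the unclustered test.** Design effect = 1 + (Σm²/Σm − 1) × ICC; actual type I error = 2[1 − Φ(1.96/√design effect)].
- 30/8/0: Σm²/Σm = (30 + 32)/46 = 1.348
- 31/6/1: (31 + 24 + 9)/46 = 1.391
- 34/0/4: (34 + 36)/46 = 1.522

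For example, 30/8/0 at ICC 0.3 has design effect 1 + 0.348 × 0.3 = 1.104. Then 1.96/√1.104 = 1.865, a two-sided tail of 6.2%.

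| Mix | ICC 0 | ICC 0.1 | ICC 0.3 | ICC 0.5 |
|---|---|---|---|---|
| 30/8/0 | 5.0% | 5.4% | 6.2% | 7.0% |
| 31/6/1 | 5.0% | 5.5% | 6.4% | 7.3% |
| 34/0/4 | 5.0% | 5.6% | 6.8% | 8.1% |

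Simulation with normal differences and a random patient effect agrees to within a few tenths of a point: about 5.0–5.5%, 6.0–6.3% and 7.0–7.2% in the first two mixes, and up to about 8% at ICC 0.5 in the third. The Wilcoxon test behaves similarly, at 6.6–7.6% for ICC 0.3–0.5 across the first and third mixes (8,000 runs).

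**4. More men.** 80 × 0.55 = 44 positive men and 44 × 1.2 = 52.8 lesions. With 52–54 lesions in 44 men the unclustered error, extreme mixes included, is 5.4–5.7%, 6.2–6.9% and 6.9–8.2% at ICC 0.1, 0.3 and 0.5, so it does not improve.

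**5. The patient-clustered test** (cluster-robust variance, t with men minus 1 df). At 46 lesions its simulated type I error is 5.0–5.6% over all mixes and ICCs 0 to 0.5. Its power for 1.0 mm is:

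| Lesions | ICC 0 | ICC 0.1 | ICC 0.3 | ICC 0.5 |
|---|---|---|---|---|
| 46 in 38 men | 79% | 77% | 73–75% | 70–72% |
| 52–54 in 44 men | 84–85% | 82–83% | 79–81% | 76–78% |

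**6. Approach order.** Section 5.2 switches the order for every other patient. A simulation made the shared component wholly an order effect: 80 men in alternating order, 55% positive, and 82/16/2% of positive men with 1/2/3 lesions (mix assumed). At ICC 0.1, 0.3 and 0.5 type I error was 4.5%, 4.0% and 3.5% unclustered, and 4.3%, 3.2% and 2.4% clustered.

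**The case against.** The strongest reply is that the ICC may be close to zero. Both approaches aim at the same planned targets (section 4.2), so registration error may partly cancel. Anterior and posterior lesions in one man may also favour different approaches (sections 3.1 and 4.3). An ICC of 0.3 means a between-man SD of √0.3 × 2.4 = 1.3 mm in the paired difference, and 0.5 means √0.5 × 2.4 = 1.7 mm; both exceed the 1.0 mm effect sought. At ICC 0 to 0.1 the clustered test gains little. All of this stands, and it is why the point is a modest one.

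A reader might infer that a man's lesions are correlated because they share one approach order. The documents do not support that as a cause of inflation. Order alternates by patient, so its fixed effect nearly cancels in the mean while still adding to the estimated variance, and both tests become conservative (step 6). The average shift from repositioning comes before whichever approach is second, so it behaves the same way. Only random man-to-man variation around that average can raise type I error.

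A reader might also infer that the trial is underpowered. At 55% detection and ICC 0.3 the clustered test has 79–81% power from 80 men, which is the planned level. That margin is not assured. The plan gives "approximately 55% and 95% cancer detection rate among patients with MRI suspicion scores of 4 and 5, respectively" but no rate for score 3 lesions, which are eligible, and the 80 also covers screen failures. If 10 of the 80 were lost (an assumption), 70 × 0.55 × 1.2 = 46.2 lesions. This is a reason to state the power, and it does not show that enrolment must rise.

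**Conclusion.** The point holds as a cheap improvement. Section 4.5 uses methods for independent pairs on data that it expects to be mildly clustered. If the paired difference varies randomly between men, the planned test is modestly anti-conservative: about 5.0–5.5%, 6.0–6.4% and 7.0–7.3% at ICC 0.1, 0.3 and 0.5 when multi-lesion men mostly have two lesions. About 8% arises only at ICC 0.5 when all of them have three. At ICC 0 there is no inflation.

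These sizes rest on assumed ICCs, assumed lesion mixes and normally distributed differences. The documents give neither the ICC nor the mix. A claim of serious inflation would go beyond them.

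**What to change.** In section 4.5, keep the per-lesion mean transperineal-minus-transrectal difference in largest CCL as the primary estimate. Take its standard error and test with the patient as cluster: cluster-robust variance and a t reference with number of men minus 1 degrees of freedom. Add a patient-level sign-flip test, which reverses all of a man's differences together, as the robustness check; the ordinary Wilcoxon test ignores clustering just as the t test does.

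State an assumed ICC and the power of that same test, both at 46 lesions and at the number expected from 80 men. At ICC 0.3 these are about 73–75% and 79–81% (52–54 lesions, 55% detection).

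The cost is a few sentences and slightly more analysis work, with no change to conduct or enrolment. At ICC 0 the clustered test loses under 1 point of power. Otherwise standard errors widen by √design effect: about 2–3%, 5–8% and 8–12% at ICC 0.1, 0.3 and 0.5. If there is a real order effect, the clustered test is somewhat more conservative than the planned one.

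The rule for which lesions enter, the CCL given to a negative approach, and the unit for cancer detection rate and logistic regression are separate matters, outside this point.
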